8.4. Treatment of overdose

For this study, any dose of study intervention greater than 1.9 μg , 3.75 μg , or 7.5 μg given outside of the Study Day 18 to Study Day 25 interval will be considered an overdose.

GSK does not recommend specific treatment for an overdose.

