9.5.1.2. Final analysis (Month 13)

A final data analysis will be performed at the end of study (Month 13) of all primary and secondary endpoints based on the clean data, including evaluations of:

- Immunogenicity at all measured time points (Days 1, 22 and 43).
- Solicited administration site events and solicited systemic events data reported 7 days after each vaccination (Day 1 to Day 7 and Day 22 to Day 28).
- Unsolicited AEs and MAEs reported up 21 days after each vaccination. **(Amended 22 February 2022)**
- Concomitant medications reported up to ***21 days after each vaccination. (Amended 22 February 2022)***
- SAEs, pIMDs, and withdrawals due to AEs collected throughout the entire study.
- Pregnancies throughout the entire study.

An integrated clinical study report containing all data will be written and made available to the investigators.

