10.3.8.1. Time period for collecting and recording AEs

All AEs that occur within 21 days following administration of each dose of study vaccine/product must be recorded into the appropriate section of the eCRF, irrespective of intensity or whether or not they are considered vaccination-related. **(Amended 22 February 2022)**

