4.6.6 Modified Per Protocol Set (mPPSx)

Modified Per Protocol Set 1 (mPPS1)

- *The mPPS 1 is a subset of FAS 1. The mPPS 1 includes all FAS 1 participants with no major protocol deviations (check major protocol deviations definition in [Section 5.2](#)) that lead to exclusion at or prior to Visit 3 (Day 43). The time window between Visit 1 and Visit 2 that is permitted for inclusion in this analysis set is 18-32 days. The time window between Visit 2 and Visit 3 that is permitted for inclusion in this analysis set is 14-32 calendar days.*

All major protocol deviations which lead exclusion from PPS1 will also lead exclusion from mPPS1. Only the major protocol deviations related to sample collection date or vaccination date outside to the intervals described above will not lead exclusion from mPPS1.

Modified Per Protocol Set 2 (mPPS2)

- *The mPPS 2 is a subset of FAS 2. The mPPS 2 includes all FAS 2 participants with no major protocol deviations that lead to exclusion at or prior to Visit 2 (Day 22). The time window between Visit 1 and Visit 2 that is permitted for inclusion in this analysis set is 18-32 days.*

Major protocol deviations leading to exclusion are described in Section 5.2 and the Study Deviation Rules document and will be finalized prior to the interim analysis defined in Section 10.2.

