Protocol Deviation	Enr	Rand	Exp	FAS1	FAS2	PPS1	PPS2	mPPS1	mPPS2	MNPPS1	MNPPS2	MNmPPS1	MNmPPS2
Invalid informed consent or fraud in data	X	X	X	X	X	X	X	X	X	X	X	X	X
Incorrect treatment number provided at V2						X		X		X		X	
Unblinding of subject by sponsor/CRO personnel not done per study procedures at V1						X	X	X	X	X	X	X	X
Unblinding of subject by sponsor/CRO personnel not done per study procedures at V2						X		X		X		X	
Investigational vaccine administrated at V1 Day 1 even though subject met exclusion						X	X	X	X	X	X	X	X
Persistent inadequate source documents management after re-education**							X		X		X		X
Vaccine temperature deviation at V1						X	X	X	X	X	X	X	X
Vaccine temperature deviation at V2						X		X		X		X	
Inclusion/Exclusion criteria not meet						X	X	X	X	X	X	X	X
Study vaccine dose not administered according to protocol for V1: Wrong site/route injection/, wrong reconstitution, incorrect volume, Expired vaccine administered						X	X	X	X	X	X	X	X
Study vaccine dose not administered according to protocol for V2: Wrong site/route injection, wrong reconstitution, incorrect volume, Expired vaccine administered						X		X		X		X	

Protocol Deviation	Enr	Rand	Exp	FAS1	FAS2	PPS1	PPS2	mPPS1	mPPS2	MNPPS1	MNPPS2	MNmPPS1	MNmPPS2
Subsequent vaccine administered while contraindicated at V1						X	X	X	X	X	X	X	X
Subsequent vaccine administered while contraindicated at V2						X		X		X		X	
Incomplete treatment course V1						X	X	X	X	X	X	X	X
Incomplete treatment course V2						X		X		X		X	
Vaccination date at V2 done outside of the interval between V1 and V2 of 18-25 Days						X				X			
Vaccination date at V2 done outside of the interval between V1 and V2 of 18-32 Days									X			X	
Serological results collected but not available at V1						X	X	X	X	X	X	X	X
Blood sample at V1: not taken, not available, low serum volume, Lab error (spinning ...), temperature deviation						X	X	X	X	X	X	X	X
Blood sample at V2: not taken, not available, low serum volume, Lab error (spinning ...), temperature deviation					X*		X		X		X		X
Blood sample at V3: not taken, not available, low serum volume, Lab error (spinning ...), temperature deviation				X*		X		X		X		X	
Blood sample collection at V2 done outside of the interval between V1 and V2 of 18-25 Days							X				X		

Protocol Deviation	Enr	Rand	Exp	FAS1	FAS2	PPS1	PPS2	mPPS1	mPPS2	MNPPS1	MNPPS2	MNmPPS1	MNmPPS2
Blood sample collection at V2 done outside of the interval between V1 and V2 of 18-32 Days									X				X

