7.2.1 Compliance

The number and percentage of participants who received any study vaccination will be presented, as well as the number and percentage of participants who received all expected vaccinations during the study and the number and percentage of participants who withdrew from study vaccine. A participant has withdrawn from study vaccine if vaccination was administered at Visit 1, no vaccination was administered at Visit 2 and the participant has data recorded for at least one of the following: Telephone Contact Day 8 or Visit 2.

In addition, the number and percentage of participants who did not receive all vaccinations with reason (including participants who received a partial vaccination) will be displayed by visit. All study groups and age group are expected to receive 2 vaccinations; one at Visit 1 and one at Visit 2.

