9.1.2 Unsolicited Adverse Events

An unsolicited AE is an AE that was not solicited using a participant Diary and that was spontaneously communicated by the participants or a solicited administration site or systemic event that meets the criteria described in Section 0. Solicited events lasting more than 7 days after vaccination (including the day of vaccination) are also recorded as unsolicited AEs.

The original verbatim terms used by investigators to identify AEs in the Adverse Events page of the eCRF will be mapped to preferred terms (PT) using MedDRA, version to be delineated in the CSR. The AEs will then be grouped by MedDRA according to system organ class (SOC).

The following summaries will present the event count, number and percentage of participants reporting each AE and will be presented by SOC, PT, and maximum relationship to study intervention for each study group, grouped by 21 days post-vaccination at any visit and then by 2 time points (at the final analysis): 21 days post-vaccination at Visit 1, and 21 days post-vaccination at Visit 2:

- Any unsolicited AE
- Any severe unsolicited AE (grade 3)
- Any related unsolicited AE
- Any severe related unsolicited AE (grade 3 related)
- Unsolicited MAEs
- Any AEs with MAEs
- Any related AEs with MAEs

Additional summaries will present the number and percentage of participants reporting AEs in the following categories and will be presented by SOC and PT for each study group and age group from Day 1 through the Day 43 visit and from Day 1 through the end of study:

- SAEs
- AEs leading to withdrawal from study drug (through Day 22 only)
- AEs leading to withdrawal from study
- MAEs (within 21 days post each vaccination)
- pIMDs

Data listings of all AEs will be provided by participant. In addition, AEs in the categories above will be provided as listed data.

Missing data will be handled as described in Section 4.5.

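### The Day 22 cut-off on the table of AEs leading to withdrawal from study vaccine (SAP 9.1.2) is shorter than the plan's own dose 2 window

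*SAP*

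**What the plan says.** SAP 9.1.2 lists a set of AE summaries by system organ class (SOC) and preferred term (PT), to be reported "from Day 1 through the Day 43 visit and from Day 1 through the end of study". One line has its own, shorter limit: "AEs leading to withdrawal from study drug (through Day 22 only". The line for AEs leading to withdrawal from the study has no such limit.

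The dose 2 window is longer than that. SAP Table 9 makes a dose 2 date a reason for exclusion from PPS 1 under "Vaccination date at V2 done outside of the interval between V1 and V2 of 18-25 Days", and Protocol 8.4 gives the same window in study days ("given outside of the Study Day 18 to Study Day 25 interval"). For the modified sets, SAP 4.6.6 states: "The time window between Visit 1 and Visit 2 that is permitted for inclusion in this analysis set is 18-32 days". The rationale in the Amendment 2 summary of changes is that more visits than expected fell outside their windows.

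Two neighbouring rules matter:

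- **Vaccine-withdrawal count.** SAP 7.2.1 counts a participant as withdrawn from study vaccine if dose 1 was given, "no vaccination was administered at Visit 2 and the participant has data recorded for at least one of the following: Telephone Contact Day 8"; the other contact that qualifies is the second clinic visit. Protocol 7.1 calls anyone who has not had every planned dose a discontinuation.
- **AE recording.** Protocol 10.3.8.1 states: "All AEs that occur within 21 days following administration of each dose of study vaccine/product must be recorded into the appropriate section of the eCRF". Protocol 9.5.1.2 nevertheless puts into the Month 13 analysis "SAEs, pIMDs, and withdrawals due to AEs collected throughout the entire study".

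**The concern.** A table of AEs that stopped the vaccine should cover the whole time in which the vaccine can be stopped, that is, from dose 1 until dose 2 is given or ruled out. A fixed Day 22 limit does this only for participants whose dose 2 falls on or before Day 22. Protocol 7.1.1 lets dose 2 be postponed within the permitted interval for acute illness or fever, so some participants will still be waiting for it after Day 22.

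Safety is a co-primary objective, and Protocol 9.4.3.2 asks for a separate summary of AEs leading to withdrawal. Any omission can only lower the count in that summary. The wording is also open to two programmings, Study Day 22 or the Visit 2 contact, which could give different tables.

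**Working it through.** The plan states no figure on this point, so there is nothing to reproduce. The check counts days and compares rules.

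**1. Study day.** SAP 4.2 defines it, on or after dose 1, as assessment date − first dose date + 1. Study Day 22 is therefore 21 days after dose 1.

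**2. Permitted dose 2 days after a literal Day 22 cut.** Protocol Table 2 and Section 8.4 give the window in study days. SAP Table 9 and SAP 4.6.6 say only days, so elapsed days are shown as a second reading (elapsed day d is Study Day d + 1).

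| Window | Study Days | Days in window | Days after Day 22 |
|---|---|---|---|
| 18–25 as study days | 18–25 | 25 − 18 + 1 = 8 | 25 − 22 = 3 |
| 18–25 as elapsed days | 19–26 | 8 | 26 − 22 = 4 |
| 18–32 as study days | 18–32 | 32 − 18 + 1 = 15 | 32 − 22 = 10 |
| 18–32 as elapsed days | 19–33 | 15 | 33 − 22 = 11 |

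If Day 22 means Visit 2, no in-window day is cut. The 18–32 window decides membership of the modified sets only. The AE tables use the Exposed Set, which has no visit window, so Day 32 shows how late a dose the plan foresees and is not a boundary of the safety analysis.

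**3. Which events are affected.** SAP 4.5 assigns unsolicited AEs to periods by start date. An illness that began by Day 22 stays in the table even if the decision on dose 2 came later. What drops out is a new onset after Day 22 in someone still waiting for dose 2.

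**4. What still shows such a case.** Protocol 7.1 puts the reason for stopping the vaccine on the eCRF, with AE options and no day limit. SAP 5.1 (disposition) and SAP 7.2.1 (compliance) tabulate it, and SAP 9.1.2 lists all AEs. SAEs and pIMDs have their own tables to the end of study. What is missing is the SOC/PT entry in the vaccine-withdrawal table.

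**5. Recording window.** Protocol 10.3.8 has unsolicited AEs entered on the diary for the day of vaccination and 20 more days: 1 + 20 = Study Day 21. Protocol 10.3.8.1, read as 21 days after the dose, ends on 1 + 21 = Study Day 22. Under the general rule alone, the uncovered stretch before a pending dose 2 is 25 − 22 = 3 or 25 − 21 = 4 days to Day 25, and 32 − 22 = 10 or 32 − 21 = 11 days to Day 32.

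Other statements go further:

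- SAP 3.1 records AEs leading to withdrawal from consent to Month 13.
- Protocol 9.5.2 and SAP 10.4 name AEs leading to study withdrawal among the data still collected after Day 43.
- SAP 4.5 assigns AEs leading to study withdrawal to the entire study.

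Against these, the Table 1 row for unsolicited AEs ends at Visit 3, and Protocol 9.4.3.2 restricts its AE analysis to onsets within 21 days of the latest dose. SAP 3.1 does not settle the matter, because it also carries medically attended AEs to Month 13, whereas SAP 3.2.1 limits them to 21 days after each dose.

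**6. Compliance count.** SAP 7.2.1 leaves out of the vaccine-withdrawal count only participants with data at neither the Day 8 call nor Visit 2. The same section still places them in its summary of participants not given every dose, with the reason. The two counts can therefore differ by exactly this group.

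**The case against.** The best defence is that Day 22 is a visit label. SAP Table 8 names the visit V2 DAY 22, the FAS 2 definition writes Visit 2 (Day 22), and SAP 9.1.1 calls the week after dose 2 Day 22 to Day 28 despite the 18–25 window. The restriction also makes sense, since after dose 2 there is no vaccine left to withdraw. This stands as a plausible reading. It does not settle the point, because the sentence that introduces the list writes Day 43 visit where a visit is meant, and this line says only Day 22.

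It can also be said that little is at stake: the day counts are not counts of participants or events, only new onsets after Day 22 matter, and the reasons are tabulated elsewhere. That is right and limits the size of the point. But the disposition and compliance tables give a reason category, not the event by SOC and PT.

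A reader might go further and infer that AEs causing later study withdrawal are lost. The documents do not support this: they state collection to Month 13, assign these events to the whole study and tabulate them to the end of study. Protocol 10.3.8.1 sets what must be recorded and does not say that nothing else is.

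**Conclusion.** The point holds in a limited form, with moderate confidence. Taken as a study day, the cut-off makes one planned safety table incomplete for new onsets on Days 23–25 (3 of 8 permitted days), or up to Day 32 under the modified-set window (10 of 15). Taken as Visit 2, it needs only to be stated. The documents give no basis for estimating how many events this would be.

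The vaccine-withdrawal count in SAP 7.2.1 is narrower than the definition in Protocol 7.1, but only by participants with neither contact. The 21-day wording and the Month 13 statements are unreconciled; that is a matter of consistency, not evidence of missing data.

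Three further inferences should not be drawn:

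- **That anyone who stops before Day 8 goes uncounted.** Someone who declines dose 2 on Day 3 but takes the Day 8 call or attends Visit 2 is counted. The compliance rule does not filter the AE table, and a Day 3 AE lies well before the cut.
- **That the bias is largest in the more reactogenic arms.** No figure supports this, and solicited reactions are collected on Days 1–7.
- **Anything about collection periods from Protocol Table 11.** Its cell contents cannot be read in the available text, so nothing here rests on them.

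**What to change.** - **SAP 9.1.2:** replace the Day 22 limit with onset from dose 1 until dose 2 is given or the decision not to give it. This works under either reading of Day 22. If Visit 2 was always meant, say so. The Action Taken field named in SAP 4.5 already identifies the events.
- **SAP 7.2.1:** delete the requirement for data at the Day 8 call or Visit 2, so that the count follows Protocol 7.1.
- **Protocol 10.3.8.1, 9.4.3.2 and the Table 1 unsolicited-AE row:** reconcile these with Protocol 9.5.2 and SAP 3.1 and 10.4, stating in one place the collection period for AEs leading to withdrawal of the vaccine or from the study. A separate schedule row would do this.

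The cost is minor SAP and schedule wording and a few extra AE entries. The eCRF fields and the telephone contacts already exist, and no dosing or visit rule changes.

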9.2 COVID-19 Assessments

Frequencies and percentages of participants with suspected, probable, or confirmed COVID-19 cases will be summarized for the Exposed Set for each study group, age group, and overall.

In addition, a summary of the following COVID-19 additional assessments will be produced on all assessments reported. with the denominator being subject (i.e. if more than one per subject, counted only once):

- Does the subject have a history of travel to or residence in a location reporting community transmission of COVID-19 disease during the 14 days prior to symptom onset?
- Did the subject visit any health care facility in the 14 days prior to symptom onset?
- Did the subject have contact with a confirmed or probable case in the 14 days prior to symptom onset?
- Were any concomitant medications taken by the subject, including experimental medications, to treat COVID-19?

Additional COVID-19 case details will be produced. The listing will include:

- Site Identifier
- Treatment
- Period
- Unique Subject Identifier
- Subject Identifier

- COVID-19 case diagnosis
- COVID-19 test performed
- Result of the COVID-19 test
- Assessments and Symptom Assessments performed
- Results of the Assessments and Symptom Assessments

Participants with COVID-19 cases or who take COVID-19 vaccine may be excluded from the per protocol analysis depending on timing of the infection or the vaccination. For example, if a participant has COVID-19 infection between Day 22 and Day 43, the participant may be excluded from analysis of Day 43 data but still be included in the analysis for Day 22 data.

The COVID-19 related protocol deviations (e.g. blood draw outside of allowed time window due to COVID-19 related restrictions of movement) will be reviewed together with other protocol deviations. Participants with major protocol deviations may be excluded from per protocol analysis sets, as described in Section 5.2.

If study procedures are modified due to special circumstances, there may be a requirement to conduct analyses that separately describe the data collected during the period of modified study procedures. If required, these analyses will be described in a separate analysis plan.

9.3 Clinical Laboratory Evaluations

Clinical laboratory measurements (e.g. clinical chemistry, hematology, and urinalysis) are not scheduled to be taken during the study; however, clinical laboratory tests may be done and the results obtained as part of critical care or follow-up due to the occurrence of MAEs, SAEs, or pIMDs during the study. The investigator must review the laboratory report, document that he/she did so, and record any clinically relevant changes occurring during the study in the eCRF. Clinically significant abnormal laboratory findings are those which are associated with an underlying disease judged by the investigator to be more severe than expected for the participant's condition.

Should any clinical laboratory tests be performed during the study for a participant, abnormal laboratory findings or other abnormal assessments that are judged by the investigator to be clinically significant will be recorded as an AE or SAE if they meet the definition of an AE or SAE and will be included in AE/SAE summaries.

9.4 Physical Examination and Vital Signs

At a minimum, temperature and vital signs (e.g. heart rate and respiratory rate, blood pressure) must be collected. Participants will undergo a physical examination and vital signs are to be taken prior to the first vaccination and will consist of 1 pulse and 1 blood pressure measurement. Blood pressure and pulse measurements will be assessed by a completely automated device on Day 1 only. Manual techniques will be used only if an automated device is not available. Collected information will be recorded in the eCRF. Blood pressure and pulse measurements will be listed only.

Summary statistics (mean, SD, minimum and maximum) for pre-vaccination body temperature at each visit will be presented by study group and age group for the Exposed Set. Pre-vaccination vital signs and body temperature will be listed for the Exposed Set.

9.5 Pregnancy

Female participants of childbearing potential will have a urine pregnancy test prior to any study vaccine(s) administration.

Pregnancy test results will be displayed in a listing for the Exposed Set. Listings of pregnancy will also be generated.

10 Sequence of Analyses

10.1 iSRC Review

At least 2 iSRC reviews are planned, as described in Section 3.1. For each iSRC review, a subset of unblinded Tables, Listings and Figures (TLFs) from the main analysis will be generated by PPD and delivered to the iSRC team at GSK for their review. The TLFs required for these reviews are detailed separately in the TLF Table of Contents (ToC). Details regarding the timing and scope of iSRC reviews will be provided in the iSRC charter.

The iSRC will review the following data:

1. Participant demographic data
2. Adverse Events (AEs) / Serious Adverse Events (SAEs), including Council for International Organizations of Medical Sciences (CIOMS) reports, including listings for:
 - All AEs
 - Potential immune-mediated diseases (pIMDs)

- Fatal SAEs
- AEs/SAEs/pIMDs leading to permanent discontinuation from study treatment or withdrawal from the study
- AE/SAEs/pIMDs causally related to study vaccine

3. Participant Disposition listing (number of subjects vaccinated, withdrew from the study, withdrawal reasons)
4. Other information as deemed necessary by the study team/iSRC

The Safety Review Team (SRT) will review the same safety data, but in a blinded manner.

10.2 Analysis at Day 43

An interim analysis will be performed on data collected through the Day 43 visit. This interim analysis will provide intervention-level unblinded summaries for GSK, Biomedical Advanced Research and Development Authority, and regulatory agency review, and no individual unblinding data will be provided.

An analysis will be performed on data collected through the Day 43 visit. Elements will include:

- Analyses of cleaned immunogenicity data through the Day 43 visit will be conducted.
- Analyses of cleaned solicited administration site events and solicited systemic events data collected during a 7-day follow-up period (Day 1 to Day 7) after each vaccination will be conducted.
- Analyses of unsolicited AEs and MAEs up to 21 days post each vaccination presented overall per subject on as clean as possible data.
- Analyses of SAEs, pIMDs, pregnancies and withdrawals due to AEs collected up to the Day 43 post-vaccination visit will be carried out.
- Blinded listing of pregnancies and withdrawals due to AEs collected up to the Day 43 post-vaccination visit will be presented.
- Results will be presented in a Day 43 statistical report. Access to individual intervention codes will be restricted to the designated unblinded statisticians in charge of the analysis. No individual listings or data with the participants' identifying information will be disseminated. Listings of final data will be provided with the Month 13 report.

All analyses will be performed on data that has been cleaned and locked. The possibility of post-analysis changes to data evaluated at Day 43 exists, since data

collection and data entry may continue through Month 13. All final data will be presented in the listings provided at Month 13.

10.3 Final Analysis at Month 13

A final data analysis will be performed at the end of study (Month 13) of all primary and secondary endpoints based on the clean data, including evaluations of:

- Immunogenicity at all measured time points (Days 1, 22 and 43).
- Solicited administration site events and solicited systemic events data reported 7 days after each vaccination (Day 1 to Day 7 and Day 22 to Day 28).
- Unsolicited AEs and MAEs reported up to 21 days after each vaccination.
- Concomitant medications reported up to 21 days after each vaccination.
- SAEs, pIMDs and withdrawals due to AEs collected throughout the entire study.
- Pregnancies throughout the entire study.

An integrated CSR containing all data will be written and made available to the investigators.

10.4 Statistical Considerations for the Analysis at Day 43

Since the primary immunogenicity endpoints for the study will be complete by the Day 43 visit (collection past Day 43 includes only assessments for unsolicited AEs leading to study withdrawal, SAEs and pIMDs), no statistical consideration for multiplicity will be given to account for changes in the results reported at the interim analysis compared to the final analysis. For the primary immunogenicity analysis, which will be reported at Day 43 the overall type I error rate is fixed at 5% (two-sided intervals) and a Bonferroni adjustment will be applied to allow simultaneous multiple comparisons of each antigen/adjuvant group. No further adjustment is needed since sequential testing will be used for each antigen/adjuvant group related to the two endpoints and to the two age categories. For the secondary immunogenicity and primary safety analyses no adjustment for multiple comparisons will be made in each antigen/adjuvant group as the CIs are provided for descriptive purposes only. No adjustment is applied for the Placebo group.

11 Changes to the Protocol Planned Analysis

The duration of solicited events will also be summarized by study group, age group and vaccination.

12 References

Center for Biologics Evaluation and Research (CBER). Guidance for Industry. Clinical data needed to support the licensure of pandemic influenza vaccines. May 2007. <https://www.fda.gov/regulatory-information/search-fda-guidance-documents/clinical-data-needed-support-licensure-pandemic-influenza-vaccines>.

Food and Agriculture Organization of the United Nations (FAO). Agriculture and Consumer Protection Department. Animal Production and Health. H7N9 situation update. Avian Influenza A (H7N9) 4 September 2019. http://www.fao.org/ag/againfo/programmes/en/empres/h7n9/situation_update.htm. Accessed 2 October 2019.

World Health Organization (WHO). Avian Influenza Weekly Update Number 694. 20 September 2019. https://www.who.int/docs/default-source/wpro---documents/emergency/surveillance/avian-influenza/ai-20190920.pdf?sfvrsn=30d65594_36. Accessed: 2 October 2019

